6.2.1 Telemedicine Contacts

Telemedicine contacts may be via a straightforward phone call between the patient and an appropriately qualified member of the Investigational Site or via a video call. They should be performed as indicated in the [Flow Chart](#) but may also be performed at any time during the course of the trial to support patients with the home sampling and/ or following up on AEs or trial medication compliance.

In the event of force majeure or other disrupting circumstances, where a patient is not able or willing to come to the site for a trial visit, the following assessments can be done remotely: collect and assess adverse events, concomitant therapies, assess trial medication compliance and review safety laboratory results.

6.2.2 Home Visits

Home visits (i.e. by a nurse or physician) can be used to reduce the burden of participation on patients, and also to encourage participation following the COVID-19 or similar pandemic in case a patient is otherwise not able to travel to the site. They may be performed at the visits indicated in the [Flow Chart](#), unless the patient prefers to attend the Investigational Site for the visit.

To support visits performed at the patient's home, direct shipment of the trial medication will be managed by the site directly, for example via a courier, as permitted by local regulations. All unused trial medication from the previous visit(s), including empty package material, will be shipped from the patient's home to the site via courier. If needed, the laboratory kits and ancillary materials required by the nurse may also be shipped to the patient prior to the visit. Where country regulations allow, samples taken at home will be shipped from the patient's home to a central laboratory for analysis. Where this is not possible alternative arrangements will be made, e.g. samples taken to the investigational site.

If the patient reports an AE during these home visits, then it is at the discretion of the Investigator as to whether a telemedicine contact is needed to support this assessment or even if the patient should attend the site.

Home visits may be performed either by an appropriately qualified member of the Investigational Site team or by a CRO working on behalf of the sponsor. Where a CRO is used all source information will be made available/ transferred to the Investigational Site and should be reviewed by an investigator.

In the event of force majeure or other disrupting circumstances, where a patient is not able or willing to come to the site for a trial visit, the following assessments can be done at the patient's home: collection of blood and urine samples to be sent to the central lab, vital signs, weight, collection and review of paper diaries, collection of adverse events and concomitant therapies, assessment of trial medication compliance.

6.2.3 Screening and run-in period(s)

Screening Period

No trial procedures should be done unless the patient has consented to taking part in the trial. Once informed consent is obtained, the patient is considered to be enrolled in the trial. The patient should be recorded on the enrollment log and be registered in the IRT system as a screened patient before any other activities are performed. The screening period begins once the first screening procedure has been performed. Patients who do not start the Randomised Run-in Period should be registered as a screen failure in the IRT system. Patients who do not fulfil all eligibility criteria for a reason that later resolves and allows eligibility criteria to be met, may be re-screened. Re-screening will only be allowed once.

The footnotes to the [Flow Chart](#) provide details about when screening procedures may be repeated and when re-screening is allowed.

During the screening visit, demographics information will be collected. This includes:

- age on the day of informed consent (in years)
- Sex (male, female in order to describe the participant's sex at birth),
- For women: confirmation of childbearing potential in order to characterise the patient population and as a basis for contraception requirements
- Ethnicity and race in order to sufficiently characterise the patient population, to support possible subgroup analyses if needed and to support the calculation of the kidney function via the CKD EPI formula, unless not acceptable according to local regulations.

Randomised Run-in Period

The Randomised Run-in Period is 8 weeks. At the start of this period, patients will be randomised to receive empagliflozin or matching placebo. All visit procedures should be completed as indicated in the [Flow Chart](#).

6.2.4 Treatment period(s)

The Treatment Period is 14 weeks. During this period, patients will receive one of three doses of BI 690517 or placebo, in combination with Empagliflozin or matching placebo assigned during the run-in period. All visit procedures should be completed as indicated in the [Flow Chart](#).

6.2.5 Early discontinuation of Treatment

Patients who discontinue empagliflozin/placebo prematurely during the Run-In Period and who do not withdraw their informed consent; and patients who discontinue both empagliflozin/placebo and BI 690517/placebo during the Treatment Period and who do not withdraw their informed consent, should return for an End of Treatment (EoT) visit.

If the patient prematurely discontinues empagliflozin/placebo during the Run-In Period:

- If the patient has stopped taking empagliflozin/placebo the day of a scheduled visit or one day prior, the scheduled visit should be performed as an EoT Visit. Empagliflozin PK and safety samples should be collected. Biomarker, BI 690517 PK, aldosterone and optional biobanking samples do not need to be collected.
- If early discontinuation does not coincide with a scheduled visit, the patient should return for an EoT visit. PK, aldosterone, biomarker and optional biobanking samples do not need to be collected, but all safety assessments must be performed as indicated in the [Flow Chart](#).
- The 24-hour urine sample prior to EoT does not need to be collected.

If the patient prematurely discontinues empagliflozin/placebo and BI 690517/placebo during the Treatment Period:

- If the patient has stopped taking trial drugs the day of a scheduled visit or one day prior, the scheduled visit should be performed as an EoT Visit. All samples including PK, aldosterone profile and all biomarkers should be collected in addition to safety samples.
- If the early discontinuation does not coincide with a scheduled visit, the patient should return for an EoT Visit. PK, aldosterone, biomarker and optional biobanking samples do not need to be collected, but all safety assessments must be performed as indicated in the [Flow Chart](#).

After the EoT visit, all patients will start the off-treatment Follow-up Period (see [section 5.2.6](#)).

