		1 ²	2	3	3.1 Home sampling without visit	4	5 ³		6	7	8	9	9.1 Home sampling without visit	9.2 Home sampling without visit	EoT ⁴	FUp1 ⁵	FUp1.1 Home sampling without visit ⁷	FUp1.2 Home sampling without visit ⁷	FUp2 ²⁷
Visit ¹																			
Visit may be conducted at patient's home ⁶					X		X				X								X
Telemedicine Contact ⁷			X	(X)							(X)	(X)				(X)	(X)		
Weeks (overall)	-11	-8	-4	-2	-1	0	1	2	6	10	12	13	14	15	16	17	18		
Day ²⁹	-77	-56	-28	-14	-7	1	8	15	43	71	85	92	99	106	113	120	127		
Time window for visits (days) ²⁹	Up to 21 days before Visit 2	+/- 2	+/- 2	+/- 2	+ 2	none		+/- 2	+/- 2	+/- 3	+/- 3	+/- 2	+/- 2	+/- 2	+3	+/- 2	+/- 2	+/- 3	
						Pre-dose	Post-dose												
Serum cortisol ¹⁴	X					X	X ¹⁵	X	X	X	X			X	X				X
Biomarker sampling (serum, plasma, urine)		X				X				X				X					X
Pharmacogenomic sampling						X ¹⁷													
Optional biobanking sampling (serum, plasma, urine) ¹⁸		X				X			X					X					X
Pregnancy test ¹⁹	X		X			X			X	X				X					X
Spot urine (UACR) ²⁰	X																		
Train patient on FMV and 24-hour urine sampling	X																		
Dispense urine container for FMV urine sampling	X	X			X				X	X	X				X				
UACR First Morning Void ²¹		X		X	X	X			X	X	X	X	X	X		X	X	X	
Dispense urine container for 24-hour urine sampling					X						X								
24-hour urine sample ²¹						X								X					
Paper diary handout ²²		X			X		X	X	X	X	X								
Collect and review paper diary					X	X		X	X	X	X			X					

Trial Period	Screening	Randomised Run-in Period				Treatment Period									Follow Up Period			
Visit ¹	1 ²	2	3	3.1 Home sampling without visit	4	5 ³		6	7	8	9	9.1 Home sampling without visit	9.2 Home sampling without visit	EoT ⁴	FUp1 ⁵	FUp1.1 Home sampling without visit ⁷	FUp1.2 Home sampling without visit ⁷	FUp2 ²⁷
Visit may be conducted at patient's home ⁶					X		X				X							X
Telemedicine Contact ⁷			X	(X)								(X)	(X)			(X)	(X)	
Weeks (overall)	-11	-8	-4	-2	-1	0	1	2	6	10	12	13	14	15	16	17	18	
Day ²⁹	-77	-56	-28	-14	-7	1	8	15	43	71	85	92	99	106	113	120	127	
Time window for visits (days) ²⁹	Up to 21 days before Visit 2	+/- 2	+/- 2	+/- 2	+ 2	none		+/- 2	+/- 2	+/- 3	+/- 3	+/- 2	+/- 2	+/- 2	+3	+/- 2	+/- 2	+/- 3
						Pre-dose	Post-dose											
Randomisation (via IRT)		X				X												
Dispense study drug(s) (via IRT)		X				X		X	X	X								
Administer Empa/ matching placebo during visit ²³		X			X	X	X	X	X	X				X				
Administer BI 690517 / matching placebo during visit						X	X	X	X	X				X				

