³Visit 5 should be no more than 7 days after Visit 4. Where the patient does not meet the additional inclusion criteria 13 and 14 based on lab tests performed at Visit 4, the eGFR and potassium cannot be re-tested and the patient should permanently discontinue the study. In case of unexpected delay of Visit 5, a repeat safety sample must be taken to obtain potassium and eGFR results needed to confirm eligibility for the Treatment Period.

⁴In case a patient needs or wishes to terminate all trial treatment prematurely and if the patient agrees, the patient should undergo the procedures for End of Treatment (EoT). Please see [section 6.2.5](#) for details.

⁵Follow-up Visit 1 (FU1) must always take place at least 7 days after the EoT visit.

⁶These visits can either be performed at the Investigational site or at the patient's home. All local approvals for this must be in place and confirmed by the sponsor. Consent for home visits must also be obtained from the patient. See [section 6.2.2](#) for further details.

⁷There are various ways that Telemedicine contacts (phone call or video call) can be used during this trial:

1. Telemedicine contact to provide support for patient's urine sampling. Before the patient does their first UACR sampling at home the investigational site staff should contact the patient to ensure the patient is comfortable with the sampling process. The other timepoints marked as '(X)' are suggested times to contact the patient if they are shipping samples directly from home to ensure they understand the instructions given to them. The site may, at their discretion, offer support with further home sampling according to the individual needs of a patient.
2. Visit 3 must be performed as telemedicine contact for all patients, unless they prefer to come to the trial site instead.
3. Phone/ video calls may also take place at any other time if needed to support the patient.

⁸Informed consent must be obtained before the first screening assessment. It can be obtained on the day of the screening visit or within 4 weeks prior to the first screening assessment. The consent discussion should include showing the patient the home sampling kits and explaining this procedure.

⁹All ECGs will be done prior to the daily dose and evaluated by the investigator or a designee. See [section 5.2.4](#).

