Visit	1	2	3	3.1 Home sampling without visit	4	5	6	7	8	9	9.1 Home sampling without visit	9.2 Home sampling without visit	EoT	FUp1	FUp1.1 Home sampling without visit	FUp1.2 Home sampling without visit	FUp2															
Week of Visit	-11	-8	-4	-2	-1	0	1	2	6	10	12	13	14	15	16	17	18															
Period	Screening			Randomised Run-In Period							Treatment Period							Follow-up														
				Start Empa/ plc Tx								Start BI 690517 / plc Tx								End Tx												
Days before visit	0	1	0	0	8 ■	7 ■	1	0	3 ³	1	0	0	0	0	1	0	1	0	15 ▲	14 ▲	8 ▲	7 ▲	3 ³	1	0	0	15 ●	14 ●	8 ●	7 ●	1	0
First Morning Void (FMV)		X	X		X	X	X	X		X	X			X	X	X	X	X	X	X	X	X		X	X		X	X	X	X	X	X
24-hour urine sample									X														X ⁴									
Bring samples to clinic visit ¹			X				X			X			X											X								X
Samples collected from home ²						X														X		X						X		X		

■ days before planned Visit 4, ▲ days before regular EoT at week 14, ● days before FUp2

¹ Samples to be brought to clinic if visit is conducted at investigational site. If visit is conducted at patient's home, samples may be picked up from home.

² When samples are picked-up from home, this will be the following day at the latest. Where collection from the patient's home is not possible, alternative arrangements will be made, e.g. samples taken to the investigational site

³ Start of 24-hour urine sample can be from the day after Visit 4 and up to 3 days before Visit 5; any time after Visit 9.2 and up to 3 days before EoT. In the event of Visit 5 or EoT visit being delayed, the 24-hour urine samples must not be older than 10 days at the time of the visit. 24-hour urine sample must be completed before FMV samples for that visit.

⁴ 24-hour urine sample not required at EOT if patient discontinues prematurely prior to start of treatment with BI 690517 / matching placebo.

Visit	Day	Time relative to administration (dose at Visit)	Time Point [hh:min]	Event	
				Drug ⁵ admin.	
2	-56	-0:30 (+ 29 /- 15 min)	-1344:30		
		0:00	-1344:00	X	
4 ²	-7	-0:30 (+ 29 /- 15 min)	-168:30		
		0:00	-168:00	X	
		0:30 (+/- 5 min)	-167:30		
		1:00 (+/- 10 min)	-167:00		
		2:00 ¹ (+ 15 min)	-166:00		
5 ²	1	-0:30 (+ 29 /- 15 min)	-0:30		
		0:00	0:00	X	
		0:30 (+/- 5 min)	0:30		
		1:00 (+/- 10 min)	1:00		
		2:00 ¹ (+ 15 min)	2:00		
6	8	-0:30 (+ 29 /- 15 min)	167:30		
		0:00	168:00	X	
7	15	-0:30 (+ 29 /- 15 min)	335:30		
		0:00	336:00	X	
8 ²	43	-0:30 (+ 29 /- 15 min)	1007:30		
		0:00	1008:00	X	
		0:30 (+/- 5 min)	1008:30		

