UACR was chosen as primary endpoint (First Morning Void collection) and secondary endpoint (responder rate) because it was shown in previous phase II trials by others in CKD that it is sensitive, differentiating different doses, broad in its dynamic range and reaching a stable plateau within a reasonable time after start of treatment. It has been accepted by authorities as dose finding biomarker in CKD. Furthermore, the change in UACR correlates with long-term clinical and patient relevant outcomes.

Since UACR is a parameter that varies intra-individually over time, multiple measurements are required at treatment period baseline and during the treatment period especially towards the end of treatment where a stable response to the drug should be achieved. UACR measurements will therefore be collected on 2 consecutive days at 3 timepoints (6 measurements in total) from Week -2 to Week 0 for treatment period baseline, and from Week 12 to Week 14 during the treatment period. Sequential collection of urine during a 4-week follow-up period may deliver exploratory results of response stability and potential rebound effects.

[REDACTED]

In order to detect and mitigate the potential risk of adrenal insufficiency and Cushing's syndrome, several measures will be implemented. An ACTH Challenge test will be performed at screening to exclude patients with adrenal insufficiency. Serum cortisol will be measured at all visits from Visit 5 until EoT and a further ACTH Challenge test will be performed if adrenal insufficiency is suspected. Furthermore, free cortisol will be measured in 24-hour urine just prior to the start of BI 690517 treatment and at the end of BI 690517 treatment to determine whether BI 690517 increases cortisol levels. Patients with adrenal insufficiency or Cushing's syndrome will be discontinued from treatment with BI 690517.

A data monitoring committee (DMC) will be established to review safety data at regular intervals. For further details see [section 8.7](#).

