An individual patient will permanently discontinue BI 690517 / placebo if:

1. The patient's serum potassium measures ≥ 6.0 mmol/L by central or any local laboratory, or ≥ 5.6 mmol/L if down-titration is considered inappropriate.

¹ Where the eGFR drop occurs before the start of BI 690517 / placebo in the Treatment Period (i.e., at Visit 5), but the result is not available until after the patient starts BI 690517/placebo treatment, the patient must still permanently discontinue all randomised study treatment, including BI 690517 / placebo.

2. The patient develops Cushing's syndrome, adrenal insufficiency (including cortisol level $<18 \mu\text{g/dL}$ 30 min (± 5 min) after ACTH application) or the patient's cortisol level is $< 3 \mu\text{g/dL}$ (82.8 nmol/L) at any point in the trial. The patient must be followed according to local guidelines until resolution of the event and the event is going to be reported to the sponsor (see [section 5.2.6.1.4](#)).

An individual patient will permanently discontinue empagliflozin / placebo if:

1. Ketoacidosis is suspected.
2. Fournier's gangrene is suspected.

If empagliflozin / placebo is permanently discontinued during the Randomised Run-In period, the patient should permanently discontinue the trial. If one of the study medications (either empagliflozin/placebo or BI 690517/placebo) is permanently discontinued during the Treatment Period / after the second randomisation at Visit 5, the patient may continue to receive treatment with the other study medication and should continue with scheduled study visits according to the [Flowchart](#).

Treatment interruption

In the following case, all randomised study medication must be interrupted:

- severe SARS-COV-2 infection

In the following cases, the empagliflozin / placebo must be interrupted:

- complicated UTI
- symptomatic volume depletion

In the following cases, the BI 690517 / placebo must be interrupted:

- serum potassium $\geq 5.6 \text{ mmol/L}$ (see [section 4.2.1.1](#))
- serum potassium $\geq 5 \text{ mmol/L}$ if the patient is unable or unwilling to return to the investigational site (see [section 4.2.1.1](#))

In these cases, trial treatment could be restarted upon recovery if medically justified, please see [section 4.1.4](#).

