5.2.5.3 Urinary free cortisol

24-hour urine will be collected by the patient in containers before visits indicated in the [FMV and 24-hour Urine Sampling Flowchart](#). Details of urine collection, processing and shipment will be provided in the Lab Manual. The patient will be given instructions and containers to collect the urine. The concentration of urinary free cortisol will be measured in the urine by the central laboratory.

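### A patient who stops BI 690517/placebo alone has no usable end-of-drug 24-hour urinary free cortisol, because the second sample stays at the Week 14 EoT visit

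*Protocol*

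**What the plan says.** Protocol section 3.2 states that free cortisol is measured "in 24-hour urine just prior to the start of BI 690517 treatment and at the end of BI 690517 treatment", with the purpose of finding out whether BI 690517 raises cortisol.

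The operational text ties the second sample to a visit instead:

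- Section 5.2.5.3: "24-hour urine will be collected by the patient in containers before visits indicated in the" urine sampling chart. That chart shows two collections only, before Visit 5 and before EoT.
- Urine chart, footnote 3: the second collection may start "any time after Visit 9.2 and up to 3 days before EoT".
- Flow Chart, row "Dispense urine container for 24-hour urine sampling": marked at Visits 4 and 9 only.

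Two places say who gets an early EoT visit in the Treatment Period. Flow Chart footnote 4 covers a patient who needs or "wishes to terminate all trial treatment prematurely and if the patient agrees, the patient should undergo the procedures for End of Treatment". Section 6.2.5 covers "patients who discontinue both empagliflozin/placebo and BI 690517/placebo during the Treatment Period". Under section 3.3.4.1, a patient who permanently stops only one of the two drugs "may continue to receive treatment with the other study medication and should continue with scheduled study visits according to the" Flow Chart.

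The same section lists the reasons for stopping BI 690517/placebo alone: raised potassium, Cushing's syndrome, adrenal insufficiency, or cortisol below 3 µg/dL.

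For patients who stop BI 690517 but continue empagliflozin, SAP 7.8.2 defines the laboratory EoT value as the nearest scheduled laboratory visit while on BI 690517.

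**The concern.** For a patient who finishes as planned, EoT and the end of BI 690517 treatment coincide, and section 3.2 is met. For a patient who stops BI 690517/placebo alone they come apart: the drug ends on the day of the stop, while the urine is collected around Week 14. Nothing in the visible text moves the collection.

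At stake is the measure that section 3.2 names for the question of raised cortisol. Serum cortisol is taken on drug at Visits 6 to 9, but the 24-hour urine has no on-drug collection between the pre-dose sample and EoT. If the EoT sample is off drug, nothing replaces it. Patients stopped for Cushing's syndrome are among those affected, and they bear most directly on the question.

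The plan recognises the same situation elsewhere. Flow Chart footnote 10 and section 5.2.5.1 tie the ACTH test, when morning cortisol is low, to premature discontinuation of BI 690517/placebo as well as to EoT.

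**Working it through.** **Inputs**

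- Nominal days (Flow Chart): Visit 6 = Day 8, Visit 7 = 15, Visit 8 = 43, Visit 9 = 71, Visit 9.2 = 92, EoT = 99.
- Start of the second collection (urine chart, footnote 3): Day 92 to Day 99 − 3 = 96.
- Residual effect period: 7 days (Protocol 6.2.6; SAP 6.1 for BI 690517).
- Visit windows (Flow Chart): Visit 6 ±2, Visit 9 ±3, Visit 9.2 ±2, EoT ±2 days.

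**Lag from the stop to the start of collection.** With the last BI 690517/placebo dose on Day D, the lag runs from 92 − D to 96 − D.

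| Last dose at | D | Lag (days) | Days past the 7-day period |
|---|---|---|---|
| Visit 6 | 8 | 84–88 | 77–81 |
| Visit 7 | 15 | 77–81 | 70–74 |
| Visit 8 | 43 | 49–53 | 42–46 |
| Visit 9 | 71 | 21–25 | 14–18 |

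The nominal range is 21 to 88 days. With visit windows, the shortest lag is (92 − 2) − (71 + 3) = 16 days and the longest is (99 + 2 − 3) − (8 − 2) = 92 days. All exceed 7 days.

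**When the Week 14 sample would still count.** On nominal days, 92 − D ≤ 7 needs D ≥ 85, and 96 − D ≤ 7 needs D ≥ 89. Only a stop in about the last two weeks of treatment leaves the sample inside the residual effect period.

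**Whether other text moves the sample**

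- Section 3.1 gives an EoT visit when trial treatment is permanently discontinued. That visit opens a 4-week off-treatment follow-up, so it cannot apply to someone still taking empagliflozin/placebo.
- Footnote 4 of the urine chart is only a waiver: "24-hour urine sample not required at EOT if patient discontinues prematurely prior to start of treatment with BI 690517 / matching placebo". It does not address a later stop of BI 690517 alone.
- Section 6.1 permits unscheduled visits, but no 24-hour urine is required at them.
- SAP 7.8.2 can only choose among scheduled on-drug laboratory visits, and none of these has a 24-hour urine.

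**Number of patients.** The documents give no rate of BI 690517-only stops. Assuming 2% to 10%, for scale only: 120 × 0.02 = 2.4 to 120 × 0.10 = 12 per dose, and 360 × 0.02 = 7.2 to 360 × 0.10 = 36 over three doses. The 120 is 60 per arm on two backgrounds, a planned completer count, so it is only a rough denominator for patients who stop.

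**The case against.** The strongest reply accepts the dates and disputes the harm.

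- *An off-drug value would be analysed as the end-of-drug value.* A reader might infer this, but the documents do not support it. SAP 7.8.2, if it covers this measure, already keeps the Week 14 value from serving as EoT. The visible SAP does not name urinary free cortisol, and some SAP sections are not shown. The certain harm is a missing value.
- *The conclusion on cortisol would be biased.* This too might be inferred, since section 4.1.2 notes that the potassium rise tends to grow with dose, so potassium stops could cluster at higher doses. No stop rate is given, and safety analyses are descriptive without testing. At least 480 planned completers still supply the before-and-after group comparison.
- *Patient safety is at risk.* Not supported. Section 3.3.4.1 requires follow-up of Cushing's syndrome and adrenal insufficiency until resolution, and serum cortisol continues at visits.
- *Most stop reasons do not match the question.* This stands. Adrenal insufficiency and cortisol below 3 µg/dL are low-cortisol events, and potassium stops are not cortisol events. Only Cushing's syndrome directly matches a question about increased cortisol.
- *Patients who stop both drugs are not clearly better served.* This also stands in part. They have an early EoT, but before Visit 9 no container has been issued for that collection.

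None of this supplies the on-drug sample. The gap between section 3.2 and the schedule remains.

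**Conclusion.** The point holds and is minor. A patient who stops BI 690517/placebo alone and remains on empagliflozin/placebo has no usable end-of-BI 690517 urinary free cortisol, unless the stop falls in about the last two weeks of treatment. No analysis rule can recover a sample that was not taken.

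This rests on two conditions: that the patient stays on empagliflozin/placebo, since stopping that drug later would bring EoT forward, and that no unscheduled 24-hour urine is collected. The number affected is unknown. The loss includes the Cushing's syndrome stops, but the documents do not show that it would change the trial's overall reading of cortisol.

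**What to change.** **Protocol 6.2.5 and the urine chart.** Add that a patient who permanently stops BI 690517/placebo alone collects the 24-hour urine as soon as possible, within 7 days of the last BI 690517/placebo dose where feasible, in place of the Week 14 sample. Issue the container at the visit or potassium recheck that decides the stop, and do the same for both-drug stops before Visit 9. If 7 days have already passed, record the end-of-BI 690517 value as missing.

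**SAP 7.8.2.** For urinary free cortisol, use this stop sample as the EoT value. List any later sample only, flagged as off-drug.

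**Cost.** One sentence in 6.2.5, one chart footnote and one sentence in the SAP; a container issued earlier; and the loss of an off-drug Week 14 value that might have shown recovery. For a BI 690517-only stop, the stop sample replaces the Week 14 one, so no collection is added.

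**Limits.** The sample is still taken after the last dose, though inside the residual effect period. Some potassium stops will stay missing: with rechecks every 72 hours during an interruption (section 4.2.1.1), a third recheck falls at 3 × 3 = 9 days, past the limit. Exposure before the sample will also vary between patients.
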